8.3 Discontinuation of Study Drug and Subject Withdrawal

The Sponsor reserves the right to discontinue this trial at any time. The investigator must discontinue subjects from the study should any of the following occur:

- Any medical condition or circumstance that exposes the subject to substantial risk and/or does not allow the subject to adhere to the requirements of the protocol;
- Any serious adverse event (SAE), clinically significant adverse event (AE), severe laboratory abnormality, intercurrent illness, or other medical condition in which, in the judgment of the investigator, continued participation in the study is not in the best interest of the subject;
- Pregnancy;
- Subject elects to withdraw;
- Requirement for other medical treatment that is excluded by the protocol;
- Subject is unblinded by the investigator;
- Failure of the subject to comply with protocol requirements or study related procedures; or
- Termination of the clinical trial by the Sponsor or by FDA.

Reason(s) for subject withdrawals as well as details relevant to the subject withdrawal will be documented. If a subject is withdrawn from the clinical trial prior to trial completion, the subject will undergo all end of study procedures.

9.0 TREATMENT OF SUBJECTS

9.1 Study Treatment

Eligible subjects will receive either top-dose VI-0521 (phentermine and topiramate extended-release capsules 15 mg/92 mg), phentermine 30 mg capsules, or placebo capsules for daily use. The duration of treatment will be 8 weeks, and the total duration of participation will be a total of approximately 12 weeks.

9.2 Allocation to Treatment

Subjects will be assigned to study treatment via an electronic data capture (EDC)/Randomization and Trial Supply Management (RTSM) System. Eligible subjects will be randomly assigned with equal probability, to daily treatment with top-dose VI-0521, phentermine 30 mg, or placebo (1:1:1 ratio). Randomization will be stratified by gender (male; female), age (< 50; \geq 50 years), and hypertensive status (no medical diagnosis of or treatment for hypertension; medical diagnosis of hypertension treated with 0-2 antihypertensive agents; or medical diagnosis of hypertension treated with 3 or more antihypertensive agents). For hypertensive patients who are being treated with fixed-dose combinations, these should be counted as 2 antihypertensive agents.

Sites will be pre-stocked with study drug corresponding to each treatment group. When study subjects qualify for randomization, site personnel will contact the EDC/RTSM through a designated website and provide the requested information about the study subject. The randomization assignment will be made, and site personnel will be instructed to dispense a specific titration blister card or treatment bottle corresponding to the treatment assignment to the study subject. Additional study drug will be shipped to sites to replace those dispensed.

9.3 Breaking the Blind

Study drug must not be unblinded during the study unless it is considered necessary by the investigator for the management of an adverse event or other medical emergency. In the event of such medical emergency, the site should contact the study designated medical monitor. The identity of the study treatment will be obtained through the EDC/RTSM and VIVUS or designee will be notified of the unblinding. Any subject whose treatment assignment has been unblinded must be discontinued from the study.

Investigators are also required to ensure that any potential serious adverse events (SAEs) are reported according to the requirements outlined in [Section 12.4.1](#) and provide a written report to VIVUS or designee within 7 days to document the reason for unblinding.

9.4 Drug Supply

Clinical supplies will be manufactured for VIVUS by [REDACTED] in accordance with current Good Manufacturing Practices. All clinical supplies will be labeled with information required by national regulations.

9.4.1 Formulation and Packaging

Study drug will consist of #0 elongated capsules filled with beads containing phentermine and topiramate extended-release, phentermine, or placebo. Doses specified for each treatment group will be achieved by varying the amounts of phentermine beads, topiramate beads, or placebo beads added to each capsule. All study treatments will be administered as a single capsule of medication to be taken in the morning.

Study drug will be packaged into titration blister cards (first 4 weeks) and treatment bottles (last 4 weeks). Each titration blister card will contain 4 columns of 8 capsules each. Each column on the blister card will be labeled with the week number (1 through 4) and will contain capsules with the dose specified for that week of treatment, as outlined in [Table 1](#). Each treatment bottle will contain 35 capsules of study drug at the treatment dosages (top dose VI-0521, phentermine 30 mg, or placebo). Each blister card or bottle will be labeled with the study number, a unique kit number, storage instructions, and spaces for the subject number and initials.

Subjects will undergo a four-week titration period with dose increases as described below until the randomized dose is reached.

Table 1 Dose Strengths by Titration Week

Assigned Doses of PHEN/TPM (mg/mg)	N	Titration Doses (mg/mg) of PHEN/TPM QD			
		Week 1	Week 2	Week 3	Week 4
Placebo	185	0/0	0/0	0/0	0/0
Phentermine 30	185	30/0	30/0	30/0	30/0
VI-0521 Top-Dose 15/92	185	3.75/23	7.5/46	11.25/69	15/92

PHEN: phentermine; TPM: topiramate; QD = once per day

9.4.2 Preparation and Dispensing

Clinical supplies provided by the Sponsor are to be dispensed only by or under the direct supervision of qualified investigators to subjects meeting the criteria for study entry and in accordance with this protocol. Assignment of study drug to study subjects will require the use of the EDC/RTSM. No other preparation of clinical supplies is required of the site staff.

9.4.3 Administration

Investigators will instruct subjects to take 1 capsule of study drug every morning with or without food. Capsules must be taken whole, and should not be broken or split apart in any manner. When dispensing titration blister cards, investigators should ensure that subjects understand that each blister card contains a 4-week supply of study drug, and that the capsules must be taken in a specific order (i.e., Week 1 before Week 2, and Week 3 before Week 4).

When dispensing study drug bottles, investigators should ensure that subjects understand that each bottle contains a 4-week supply of study drug and that each bottle contains extra capsules that should only be taken for special circumstances (e.g. capsule is accidentally dropped and cannot be retrieved or subject cannot return to the end of study visit within window). Study drug will not be dispensed until the morning of Day 2 after the ABPM device is removed following the baseline 24-hr recording and data has been confirmed to be compliant.

Subjects will be instructed to withhold dosing of study drug on study visit days until after certain procedures are completed.

9.4.4 Compliance

Subject compliance with dosing of study drug will be assessed by counting capsules that are returned by subjects at each study visit. Subjects whose actual medication consumption differs from their expected capsule consumption should be queried by site personnel about reasons for not using study drug as directed, and site personnel should implement any corrective action as necessary. Trough blood samples will also be collected at study completion, and may be used to identify subjects with compliance levels that are unacceptable for inclusion in per-protocol analyses.

Study drug must be dispensed and administered according to the procedures described herein. In accordance with applicable regulatory requirements, only subjects who are enrolled in the study may receive study drug, and only authorized members of the site staff may supply or administer the study drug.

9.4.5 Drug Storage and Drug Accountability

All unused study drug must be stored in its packaging at room temperature, 15 to 25°C (59 to 77°F), in a dry, secure area. Access to drug storage areas should be limited to the investigator and designated staff involved with the study. All used and unused drug must be maintained at the study site and made available for audits by VIVUS personnel or their designee.

It should be noted that phentermine and VI-0521 are Schedule IV controlled substances. The investigator should take all appropriate measures to control access to and dispensing of study drug.

The investigator must maintain records documenting the amount, condition and date of delivery of all study drug received from the sponsor. In addition, all drug dispensed to study subjects during the course of the study must be recorded on the appropriate accountability forms. Subjects must be instructed to return all study drug (blister cards and the bottle, even if empty) in its original packaging at each study visit and sites must make an accounting of drug use by each subject. No study drug or packaging, used or unused, may be discarded. All packaging and used and unused study drug must be returned to the sponsor upon completion of the study.

9.5 Lifestyle Counseling Guidelines

All randomized subjects will receive diet and exercise counseling at the baseline visit with support and reinforcement provided at follow-up visits. Guidelines should include advice on maintaining an appropriate healthy diet with a recommended initial caloric deficit of approximately 500 kcal per day, and at least 30 minutes of regular physical activity on most days of the week. On days when ABPM is attached, subjects should refrain from heavy exercise.

9.6 Concomitant Medications

9.6.1 Excluded Medications

Use of any of the following medications during participation in this study is prohibited:

- Tricyclic antidepressants, MAOIs, lithium, levodopa, and dopamine receptor agonists;
- Insulin, sulfonylureas (SFUs), GLP-1 receptor agonists, SGLT inhibitors for subjects with type 2 diabetes mellitus; or

- OTC, prescription medications, herbal agents and dietary supplements used to lose body weight.

9.6.2 Management of Blood Pressure

Concomitant medications used for management of blood pressure, must be fixed in number, dose, and frequency for the duration of the study unless specific “rescue” criteria are met for blood pressure.

Rescue criteria are defined as:

- Blood pressure \geq 160/100 mmHg, or;
- Blood pressure \leq 100/60 mmHg, and subjects exhibiting symptoms associated with low blood pressure, concomitant antihypertensive medications should be withdrawn or doses should be reduced.

As this study has a short (8-week) duration, and as the first post-randomization evaluation occurs after 4 weeks of treatment (half way through the study), if rescue criteria for blood pressure are met at the Week 4 visit, sites should make all reasonable efforts to keep the subject on the study, to continue taking study drug, and to have them return within 1-2 weeks for re-evaluation of their blood pressure. If rescue criteria are still met at the repeat visit, then sites should complete the final ABPM evaluation and end of study procedures. Once the final ABPM evaluation and end of study procedures have been completed, rescue therapy should be initiated, and the subject discontinued from the study.

Adverse events that require initiation or modification of antihypertensive therapy are considered events of special interest and should be clearly documented and explained to enable narratives.

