13.1.2 Method for Prevention and Treatment of Missing Values

For subjects who discontinue treatment prior to study completion, every attempt will be made to obtain end of study ABPM assessments prior to their discontinuation of treatment or initiation of changes to concomitant antihypertensive medications.

Several sensitivity analyses will be considered to explore any deviations from statistical assumptions and the impact of missing data on the conclusion of the primary analysis. The details of the sensitivity analyses will be included in the SAP.

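### Protocol 9.6.2 gives conflicting timing for antihypertensive changes when a subject meets the symptomatic low blood pressure criterion at Week 4

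*Protocol*

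**What the plan says.** Protocol 9.6.2 opens with a general rule: blood pressure medication "must be fixed in number, dose, and frequency for the duration of the study unless specific “rescue” criteria are met for blood pressure". It then lists two criteria. The high-pressure criterion has no action attached. The low-pressure criterion, which also requires symptoms, has one: "concomitant antihypertensive medications should be withdrawn or doses should be reduced".

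The following paragraph starts from the condition "if rescue criteria for blood pressure are met at the Week 4 visit". Sites are asked to make reasonable efforts to keep the subject in the study, "to continue taking study drug, and to have them return within 1-2 weeks for re-evaluation of their blood pressure". If criteria are still met at that repeat visit, the site completes the final ABPM and the end-of-study procedures. The last step reads: "Once the final ABPM evaluation and end of study procedures have been completed, rescue therapy should be initiated, and the subject discontinued from the study".

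Protocol 13.1.2 adds that, in subjects who stop treatment early, the end-of-study ABPM should be sought "prior to their discontinuation of treatment or initiation of changes to concomitant antihypertensive medications". SAP 7.1.7 says much the same.

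For the analysis, SAP 7.2.1 adopts a treatment policy strategy for intercurrent events and maps an early-termination ABPM to Week 8. It does not name an antihypertensive change as an intercurrent event.

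**The concern.** The low-pressure bullet and the paragraph after it can both apply to the same subject on the same day. One names a medication action with no wait. The other places the start of rescue after a repeat visit and a final ABPM. Appendix 1 schedules no other visit between randomization and Week 8, so Week 4 is where the question will mostly arise.

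Two things are at stake. The first is safety: a site with a symptomatic subject needs one instruction. The second is the data: depending on which sentence a site follows, similar subjects may contribute different kinds of measurement to the primary endpoint, and the SAP does not tell them apart.

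**Working it through.** **1. The two instructions side by side (Protocol 9.6.2)**

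| | Low-pressure bullet | Next paragraph |
|---|---|---|
| Trigger | Low pressure with symptoms | Any blood pressure rescue criterion at Week 4; high and low not separated |
| Action | Withdraw or reduce antihypertensives | Rescue therapy, not further defined |
| Timing | None stated | After a repeat visit at 1-2 weeks, final ABPM and end-of-study procedures |
| Study participation | Not addressed | Study drug continues to the repeat visit; discontinuation if criteria persist |

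**2. Does another section settle it?**

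- The general rule in 9.6.2, repeated in Protocol 6.0 and SAP 3.2, allows a change once a criterion is met and mentions no wait. This sits more easily with the bullet.
- Protocol 13.1.2 and SAP 7.1.7 want the ABPM before the change. This sits more easily with the paragraph, but it covers only subjects who discontinue treatment.
- Protocol 8.3 requires discontinuation when the investigator judges that continuing is not in the subject's interest. It is silent on when antihypertensives may change.
- Limiting the paragraph to high pressure is not supported by its trigger, because low pressure with symptoms is one of the two listed criteria.

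The timing stays open.

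**3. What reaches the analysis**

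- Medication changed at Week 4 and criterion no longer met at the repeat visit: the ABPM is taken at Week 8 on altered background medication.
- Medication held and criterion still met: the ABPM is taken at about Week 5-6 (4 + 1 to 4 + 2) on unchanged medication and counted as Week 8.

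SAP 5.4 excludes subjects from the per-protocol population for a major deviation that affects ABPM. The SAP does not say whether the first case is such a deviation.

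**4. Possible size**

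The plan's own figure first. Inputs from Protocol 13.2: SD 10 mmHg, difference 3 mmHg, two-sided alpha 0.05, power 80%, dropout 5%.

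- n = 2 × (1.960 + 0.8416)² × 10² / 3² = 174.4, so 175 per group.
- 175 / 0.95 = 184.2, so 185 per group. The stated figure reproduces. (The exact t-test gives 176, inflated to 186, which is practically the same.)
- Evaluable per group: 185 × 0.95 = 175.75, about 176.
- SE of a difference: 10 × √(2/176) = 1.07 mmHg.
- Power with no shift: Φ(3/1.066 − 1.960) = 80.4% (80.1% by the exact t-test).

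Now the assumed inputs, which the documents do not give: a proportion p of VI-0521 subjects has antihypertensives reduced before the analysed ABPM, and their 24-hour SBP rises by r. Then shift = p × r and power = Φ((3 − shift)/1.066 − 1.960).

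| p | r (mmHg) | Shift (mmHg) | Power |
|---|---|---|---|
| 1% | 5 | 0.05 | 79.0% |
| 1% | 10 | 0.10 | 77.7% |
| 2% | 5 | 0.10 | 77.7% |
| 2% | 10 | 0.20 | 74.8% |
| 5% | 5 | 0.25 | 73.2% |
| 5% | 10 | 0.50 | 65.0% |

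These powers hold for superiority at a true difference of −3 mmHg and for non-inferiority at a true difference of 0 with the 3 mmHg margin, because the distance to the boundary is the same. The largest shift is 0.50/1.066 = 0.47 of a standard error. The table covers only the medication change, not the effect of an early recording.

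**The case against.** The strongest reply is that the section is loosely worded but not contradictory. A reader might infer that the protocol forbids any antihypertensive change until the repeat visit, so that a site cannot obey both sentences. The documents do not go that far. The Week 4 instruction speaks of staying in the study, continuing study drug and coming back; no sentence says that antihypertensives must stay unchanged in between. The bullet could name the action and the paragraph its timing. Or the bullet could stand alone for low pressure, with the paragraph supplying the action missing for high pressure. This stands as a limit on the claim. It does not remove the problem, because the text supports both readings and selects neither.

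The safety risk is also softened by the request for reasonable efforts, rather than a command, and by investigator judgment in 8.3. That stands too, though neither settles the timing.

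A reader might further infer that values recorded after a medication change enter the analysis with nothing to identify them. That is not so. Protocol 9.6.4 has every medication change recorded. SAP 6.6 summarises blood pressure medication by arm, SAP 7.3.1 summarises adverse events that lead to antihypertensive changes, and SAP 7.3.6 compares rescue across arms. What is missing is narrower: the direction of the change, its timing relative to the analysed ABPM, and its status as an intercurrent event.

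Finally, the affected group may be small. A subject must be taking antihypertensives, reach the low threshold and have symptoms, and eligibility does not require hypertension.

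**Conclusion.** The conflict in timing is real, lies within one section and is not resolved elsewhere. It should be corrected mainly because sites need one instruction for a symptomatic subject. It is written for criteria met at Week 4; for criteria met at an unscheduled contact the paragraph gives no sequence.

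The consequence for the analysis is minor and cannot be derived from the documents. Under the assumed 1-5% and 5-10 mmHg, the shift is 0.05-0.5 mmHg and power falls from about 80% to between 79% and 65%. The lower end is negligible.

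One might suspect that the ambiguity could produce a false claim of non-inferiority or superiority. If reductions in antihypertensives fall mainly on VI-0521 and raise pressure, the shift works against VI-0521, so the cost is power. That they would fall mainly on VI-0521 is an inference from the blood pressure decreases described in the protocol synopsis and 4.1. If they fell mainly on a comparator, the sign would reverse, but the documents give no ground to expect that.

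**What to change.** **Protocol.** The sponsor's clinicians should reconcile the low-pressure bullet and the paragraph after it in 9.6.2, so that each criterion has one stated sequence, consistent with 13.1.2. No clinical rule is proposed here.

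**SAP.**

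- Extend the existing summaries of blood pressure medication and rescue to show, by arm, the direction of each antihypertensive change and whether it came before the analysed ABPM.
- Name this event as an intercurrent event in 7.2.1 and keep treatment policy as the main strategy. State whether the event counts as a major deviation under 5.4.
- Optionally, add a sensitivity analysis that treats the affected values as missing. It belongs in the ITT multiple imputation of 7.2.1.1: the per-protocol population requires an end-of-study ABPM, so these subjects would otherwise drop out of it.

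**Cost.** A clarifying letter or amendment wording, one extended table and, if chosen, one further imputation run. Medication changes are already collected, so no new data are needed.

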11.3 Vital Signs

Vital signs (systolic blood pressure, diastolic blood pressure, heart rate, respiration rate, temperature) will be assessed at Screening, Randomization, Week 4, and Week 8/end of study or early termination. Subjects should be seated comfortably for at least 10 minutes prior to assessing vital signs. Heart rate and respiratory rate measurements should be made by counting events (heartbeats or breaths) for a period of 30 seconds and multiplying these values by 2 to obtain the rates per minute. A calibrated blood pressure monitor should be employed for blood pressure measurements. The same cuff should be used for the same subject across multiple visits when blood pressure is performed. The same person should perform all assessments for a given subject.

Clinic blood pressure for determining hypertension should be the average of three successive BP readings, collected at least 2 minutes apart. The mean of the three values will be recorded as the subject's blood pressure.

11.4 24-hr Ambulatory Blood Pressure Monitoring (24-hr ABPM)

At Baseline and at Week 8/end of study or early termination, 24-hr ABPM will be performed non-invasively using a validated oscillometric monitor provided by a central vendor. Blood pressure and heart rate will be measured every 20 minutes from 6:00 to 22:00 hours, and every 30 minutes from 22:01 to 5:59 hours for 24 consecutive hours, while subjects continue normal routine activities. The monitor will be attached in the morning and removed after at least 24 hours. Data will be uploaded to a computer at the end of the recording session and prior to discharging the subject from the study visit, site staff will review the data to assure that: (1) at least 80% of the readings are valid, (2) there are at least 24 hours of data, and (3) there are no more than two consecutive hours of missing data. If any of these criteria are not satisfied, subjects will be asked to repeat the assessment for an additional 24 hours. ABPM hook up will be done by qualified staff.

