12.1.4 Serious Adverse Events or Serious Suspected Adverse Reactions

As defined in the Code of Federal Regulations (21 CFR 312.32), an adverse event or suspected adverse drug reaction is considered “serious” if, in the view of either the investigator or the Sponsor, it results in any of the following outcomes:

- Death;
- A life-threatening adverse event (Note: An adverse event or suspected adverse reaction is considered “life-threatening” if, in the view of either the investigator or Sponsor, its occurrence places the subject in immediate risk of death. It does not include an adverse event or suspected adverse event that, had it occurred in more severe form, might have caused death. The determination of whether an adverse event is life-threatening can be based on the opinion of either the investigator or Sponsor.);
- Inpatient hospitalization or prolongation of existing hospitalization;
- A persistent or significant incapacity or substantial disruption of the ability to conduct normal life functions; or
- A congenital anomaly/birth defect.

Important medical events that may not result in death, be life-threatening, or require hospitalization may be considered serious when, based upon appropriate medical judgment, they may jeopardize the subject and may require medical or surgical intervention to prevent one of the outcomes listed in the definition.

For this study, blood pressure values that exceed 180 mmHg (systolic) or 110 mmHg (diastolic) should be reported as serious adverse events.

If either the Sponsor or investigator believes that the event is serious, the event must be considered serious and evaluated by the Sponsor for expedited reporting.

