12.4.1 Serious Adverse Event Reporting Requirements

If an SAE occurs, VIVUS or designee is to be notified within 1 business day of awareness of the event. In particular, if the SAE is fatal or life-threatening, notification to VIVUS or designee must be made immediately, irrespective of the extent of available adverse event information. This timeframe also applies to additional new information (follow-up) on previously reported SAEs.

In the event that the investigator does not become aware of the occurrence of an SAE immediately (e.g., if an outpatient study subject initially seeks treatment elsewhere), the investigator is to report the event within 1 business day after learning of it and document the time of his/her first awareness of the adverse event.

For all SAEs, the investigator is obligated to pursue and provide information to VIVUS or designee in accordance with the timeframes for reporting specified above. In addition, an investigator may be requested by VIVUS or designee to obtain specific additional follow-up information in an expedited fashion. This information may be more detailed than that captured on the adverse event CRF. In general, this will include a description of the SAE in sufficient detail to allow for a complete medical assessment of the case and independent determination of possible causality. Information on other possible causes of the event, such as concomitant medications and illnesses, must be provided. In the case of a subject death, a summary of available autopsy findings must be submitted as soon as possible to VIVUS or designee.

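### The Week 4 instruction in Protocol 9.6.2 to continue study drug and re-check before rescue has no upper blood-pressure limit, so it literally reaches values that 12.1.4 makes serious adverse events

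*Protocol*

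**What the plan says.** Protocol 9.6.2 holds antihypertensive medication constant: it "must be fixed in number, dose, and frequency for the duration of the study unless specific" rescue criteria are met. The high-pressure criterion is a reading of 160/100 mmHg or above. The section does not say whether one or both components must reach the limit.

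If the criteria are met at Week 4, sites are asked to do what they reasonably can to retain the subject; the aim is "to continue taking study drug, and to have them return within 1-2 weeks for re-evaluation of their blood pressure". Where they are still met at the repeat visit, the site completes the final ABPM and the end-of-study procedures. Then: "Once the final ABPM evaluation and end of study procedures have been completed, rescue therapy should be initiated", and the subject is discontinued. The reason given is that the study is short and Week 4 is the first check after randomization.

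Four other places bear on this:

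- Section 12.1.4: "blood pressure values that exceed 180 mmHg (systolic) or 110 mmHg (diastolic) should be reported as serious adverse events".
- Section 12.4.1: the sponsor or its designee is "to be notified within 1 business day of awareness of the event".
- Section 8.3: the investigator must discontinue a subject for "Any medical condition or circumstance that exposes the subject to substantial risk", and for a serious adverse event where, in the investigator's judgment, "continued participation in the study is not in the best interest of the subject".
- Section 13.1.2: for subjects who stop early, sites should try hard to obtain the end-of-study ABPM before treatment stops or antihypertensives change.

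**The concern.** The 9.6.2 instruction has a lower bound only. It is reasonable for a Week 4 value just above 160/100, but nothing in it treats 200/120 differently from 162/101. It refers to neither 8.3 nor 12.1.4, although 12.1.4 already names the level at which a pressure becomes a serious adverse event.

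What is at stake is the safety of individual subjects. Week 4 is the only scheduled visit between randomization and Week 8. The section a site would open for a high reading is the one on managing blood pressure, and its specific advice is to keep dosing. In two of the three arms the study drug contains phentermine, and Protocol 4.1 acknowledges concern about its effect on blood pressure, while reporting no increase at 7.5 and 15 mg. Section 13.1.2 pulls the same way as 9.6.2, and 12.4.1 sets a reporting clock but no treatment action.

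**Working it through.** **Does the instruction reach SAE-level values?** Rescue limits (9.6.2): 160 and 100. SAE limits (12.1.4): above 180 systolic or above 110 diastolic.

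- Read as *or*: systolic above 180 implies systolic at least 160, and diastolic above 110 implies diastolic at least 100. Every SAE-level value is therefore a rescue case. A check over integer pairs (systolic 90-240, diastolic 40-140, diastolic below systolic) found 7,695 SAE-level pairs, and all met the criterion.
- Read as *and*: 185/115 is a rescue case, but 185/95 and 150/112 are not. Those two are SAE-level, yet the fixed-medication rule would still apply to them.

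The *or* reading is the likelier one. SAP 4.3 lists systolic 160 and diastolic 100 as separate thresholds, and 12.1.4 joins 180 and 110 with *or*.

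**How long a delay does the text tolerate?** 14 days to the re-check + 1 day for the ABPM = 15 days. One repeat recording under 10.4 makes it 14 + 2 = 16 days. These are upper limits. The text does not require a wait of that length, and the re-check has no 7-day minimum.

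**How many subjects?** The documents give no mean or SD for clinic pressure, so the following is assumed: normally distributed Week 4 values, systolic mean 124-132 and SD 12-16, diastolic mean 78-82 and SD 8-11. The expected count is N × P(Z > (limit − mean)/SD), with N = 555 for all subjects and N = 2 × 185 = 370 for the two active arms.

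| Case | Systolic mean/SD | z at 180 | Diastolic mean/SD | z at 110 | Above 180, of 555 | Above 110, of 555 |
|---|---|---|---|---|---|---|
| Low | 124/12 | 4.67 | 78/8 | 4.00 | 0.001 | 0.02 |
| Mid | 128/14 | 3.71 | 80/9.5 | 3.16 | 0.06 | 0.44 |
| High | 132/16 | 3.00 | 82/11 | 2.55 | 0.75 | 3.03 |

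- *Or* reading, all subjects: the high case is 0.75 + 3.03 = 3.78 if no subject exceeds both limits, and 3.66 at a correlation of 0.5. The mid case is about 0.5.
- *Or* reading, active arms: the high case is 0.50 + 2.02 = 2.52, or 2.44 at a correlation of 0.5. The mid case is about 0.33.
- *And* reading (systolic at least 160, diastolic at least 100, and at least one above its SAE limit; bivariate normal, correlation 0.5 to 0.7), all subjects: low 0.003-0.009, mid 0.13-0.28, high 1.35-2.25. Active arms: low 0.002-0.006, mid 0.09-0.18, high 0.90-1.50.

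The plan gives no figure of its own on this point to reproduce.

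**The case against.** The strongest reply is that the protocol already deals with this. Section 8.3 is mandatory, applies throughout the study and needs no pointer from 9.6.2, which only advises and asks only for reasonable efforts. Holding a subject at 200/120 on drug for two weeks would hardly be reasonable beside a duty to discontinue for substantial risk. The opening sentence of 9.6.2 lifts the fixed-medication rule once rescue criteria are met. Its closing paragraph foresees adverse events that need antihypertensive treatment, and 12.2 notes that some events call for prompt action. Exclusion 1 in 8.2 keeps out screening pressures above 140/90, so such values should be rare.

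Most of this stands, and it defeats two stronger readings. A reader might infer that 9.6.2 contradicts 8.3 or forbids treatment; it does neither. A reader might also infer that a high value can rest on a single unconfirmed reading. But 11.3 says "Clinic blood pressure for determining hypertension should be the average of three successive BP readings, collected at least 2 minutes apart", so no lack of repeat measurement is claimed.

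What remains is narrower. Section 8.3 names no pressure, and its SAE limb depends on judgment, so an SAE-level reading does not by itself end the wait. No section gives a value above which the Week 4 instruction stops applying.

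**Conclusion.** The point holds as a minor patient-safety gap: a stated instruction lacks a ceiling, although the protocol already contains a suitable one. That it reaches every SAE-level value depends on reading 160/100 as systolic or diastolic. On the other reading, some SAE-level values fall outside rescue altogether, which the same clarification would cure.

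The expected number is about 0 to 4 of 555, mid-case about 0.5. These counts rest wholly on the assumed means, SDs and normality. The upper end needs the least favorable mean and SD for both pressures at once. The 15 or 16 days are what the wording tolerates, not a required delay or a forecast of what investigators would do.

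A reader might also infer that the rule biases the primary ABPM comparison. With so few subjects expected and discontinuation following rescue, the documents do not support that.

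**What to change.** Add to Protocol 9.6.2:

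> The high-pressure rescue criterion is met if systolic is ≥160 or diastolic is ≥100 mmHg. The 1-2 week re-evaluation does not apply if the mean of the three clinic readings exceeds 180 mmHg systolic or 110 mmHg diastolic. Such subjects are managed at once: rescue therapy may be started without waiting for a repeat visit, the event is reported under 12.1.4 and 12.4.1, and the early-termination ABPM is obtained before rescue only if the investigator judges the delay safe. Subjects who receive rescue therapy are discontinued from the study, as now.

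Make the sentence in 13.1.2 on obtaining ABPM before treatment changes subject to this rule.

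The last sentence of the new paragraph matters. If immediate rescue were allowed without discontinuation, a rescued subject could stay to Week 8 and contribute an ABPM lowered by the rescue drug. SAP 7.2.1 uses observed values under a treatment policy strategy and maps early-termination recordings to Week 8, and SAP 5.4 does not name rescue as an exclusion. Any ABPM taken after rescue should therefore be flagged and not mapped to Week 8 as an on-treatment value, with a matching sentence in SAP 7.2.1.

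Cost: a short protocol amendment with IRB approval under 17.1, a letter to sites and one SAP sentence. There is no new visit or procedure, and the wait is unchanged up to 180/110. An on-drug final ABPM may be lost in a handful of subjects at most, and with it per-protocol membership under the same-day-dose criterion in SAP 5.4.
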